### Purpose of Study

- **Primary Aim:** To assess if oral Methenamine Hippurate (MH) in combination with cranberry capsules is superior to cranberry capsules alone in prevention of UTI in patients with transient post-operative urinary retention requiring a Foley catheter after pelvic reconstructive surgery.
  - **Secondary Aims:**
    - To assess patient adherence to the interventions.
    - To assess patient satisfaction associated with the different interventions.

### Hypothesis or Research Question

- We hypothesize that daily oral MH and cranberry therapy will be a superior treatment to cranberry alone in the prevention of UTI in patients with short term indwelling Foley catheters after pelvic reconstructive surgery.

### Background

Urinary tract infections (UTIs) are one of the most common bacterial infections in women [1]. It is estimated that 1.6 billion dollars are spent on UTI treatment each year [2-3]. *Escherichia coli* (*E.coli*), a gram negative bacterium, is the most common pathogen found amongst those diagnosed with UTIs. Research suggests that 70-95% of UTIs are attributed to *E.coli* which originates from intestinal microflora [4-7]. Additionally, the more virulent strains of *E.coli* express type 1 and p-fimbriae, which aid in adhesion to the urothelium [8-12]. Antibiotics have been the mainstay of treatment of UTIs, however frequent use has increased the prevalence of antibiotic resistant organisms [3-4]. Therefore, focus has shifted to non-antibiotic therapy for UTI prophylaxis.

Methenamine Hippurate (MH) has been studied for decades due to its potential role in prevention of UTI. While not technically an antibiotic, MH works via its bacteriostatic action in the bladder. MH's breakdown products include ammonium and formaldehyde [13-15] which

are most effective at a urine pH below 5.5 [16-18]. Benefits of MH are the lack of development of resistance, and the selective nature of this drug to the urinary system only. However, MH is best used in conjunction with an acidifying agent to increase its bioavailability (such as cranberry capsules or other acidic products) [14-18].

The usage of MH has been studied in various populations, has been seen to be effective in short-term catheterization [15]. One study by Schiotz, et. al revealed that in patients after gynecological surgery that required 24 hours of Foley catheter placement had an incidence of UTI in 13.9% of patients with placebo versus 2.7% of patients using MH [19]. Although there is some evidence of benefit, a Cochrane Database review revealed there was significant heterogeneity between studies and many of these studies vary in aspects such as definition of UTI and dosage of MH. Many prior studies did not combine MH with an acidifying agent, which could also limit its efficacy [14].

The American cranberry (*Vaccinium macrocarpon*) is another non-antibacterial agent which has been widely studied [8]. Cranberries are composed of ingredients that include fructose, anthocyanidins and proanthocyanidins [8, 20]. These components are proposed to affect adhesion proteins that are expressed by bacteria, such as *E.coli*, and prevent the development of infection [8, 20, 28-30].

Usage of cranberry as prophylaxis for UTI is controversial; however, results have been favorable in the post-operative gynecological population. One such study by Foxman et al. revealed that the incidence of UTI was significantly lower in the cranberry than placebo group (19% versus 38%) after undergoing gynecological surgery [32]. Additionally, the 7 patients who required an indwelling catheter at time of discharge were found to have lower rates of UTI than placebo (1 of 3 versus 3 of 4, respectively) [32]. However, a study from our center revealed that real-time prescriptions of cranberry to postoperative patients with catheters did not significantly reduce UTI rates [33].

Post-operative urinary retention (POUR) occurs frequently in patients who undergo incontinence and pelvic prolapse surgery [34-36]. Although the definition of POUR can vary between clinicians, it is reported as 2.5-24% to as high as 43% after tension-free transvaginal mesh sling placement [34, 36, 37]. This population is also at high risk for UTI due to advanced age and menopausal status [34, 38, 39]. Finally, using a catheter longer than 2 days incurs a 2-fold increased risk of development of UTI with an estimated 5% increase in bacteriuria each day of catheterization [32, 34, 40-41].

Moreover, although the incidence of UTI after pelvic reconstructive surgery ranges from 10% to 64% [42], a retrospective review performed at our institution revealed our incidence of UTI was as high as 72% [33]. In hopes to decrease the overuse of antibiotics and decrease the likelihood of antibiotic resistance, we propose that the use of MH and cranberry can reflect a potential benefit in this population of short-term indwelling Foley catheter use and help reduce the incidence of post-operative UTI after pelvic surgery.

## Research Plan

- **Study Design**

- Randomized double-blinded placebo-controlled trial

- **Setting for the study**

- All patients will be approached for enrollment into the study if they fail their retrograde void trial (VT) after major pelvic reconstructive surgery for pelvic organ prolapse during their hospital stay
- The patients will then be randomized to either receive cranberry capsules and placebo OR cranberry capsules and Methenamine Hippurate.
- The research nurse will be blinded to the group allocation.
- Patients will be instructed to take the pills assigned to them twice daily until their repeat retrograde VT in the office (6-8 days).
- A catheterized urine specimen will be then collected on the day of the retrograde void trial on or about postoperative day 7.
- Patients will be asked to return the pill bottles at their catheter removal visit, on or about postoperative day 7.
- At the end of the retrograde VT, patients will be given a questionnaire to complete regarding their experience with the medication randomized to them and satisfaction with the medication.
- At 2 weeks postoperatively, the patients will have a clean-catch urine specimen during their routine postoperative visit and this will be recorded.
- Patients' charts will be followed until their 6-week post-operative visit.
- Symptomatic or culture proven urinary tract infections detected during the research period will be treated with the appropriate antibiotics as standard of care, based on the judgment of the treating provider.

- **Participants**

Study population is women between 18 years old and 90 years old.

Inclusion Criteria:

- Patients who undergo major pelvic organ prolapse surgery that are diagnosed with POUR via failed retrograde void trial and require an indwelling Foley catheter upon hospital discharge.

Exclusion Criteria:

- Unwillingness to participate in the study.
- Inability to understand English.
- Pregnant women
- Patient personal history of nephrolithiasis, urogenital anomaly, neurogenic bladder, chronic renal insufficiency (GFR <60 ml/min/1.73 m^2), sarcoidosis, and severe hepatic insufficiency.
- Currently (prior 3 months) undergoing medical management for recurrent UTI or interstitial cystitis
- Current antibiotic use over the last month for additional medical issues.

- Active urinary tract infection.
- Patient history of taking Warfarin (Coumadin).
- Intraoperative bladder injury or cystotomy
- Physical or mental impairment that would affect the subject's ability to take medications daily or fill out questionnaires.
- Reported allergy to any of the ingredients in the cranberry, MH, or placebo pill
- Sample Size
  - A sample size was calculated to be 88 patients in each arm based on the following:
    - A prior study by Foxman et al. evaluated incidence of UTI of patients who underwent various benign gynecological surgeries who had placement of an indwelling urinary catheter. These patients were randomized to either receive TheraCran cranberry capsules or placebo for 6-8 weeks duration [32].
    - Two group  $\chi^2$  test with a 0.050 two-sided significance level was used for sample size calculation.
    - The power was set to 80%
    - Assuming an estimated drop-out rate of 15%, the number of patient enrollment per arm was set to 104, for a total of 208 patients total
- **Data Collection**
  - **Primary Outcome:**
    - Incidence of UTIs requiring treatment in each group, diagnosed during the first (approximately) one week of short-term indwelling Foley catheter in the post-operative period after undergoing major pelvic reconstructive surgery.
  - **Secondary Outcome:**
    - Adherence to the medication regimen provided
    - Patient satisfaction with medication regimen provided
    - Adverse effects that patients encountered during study period
    - Number of patients who are diagnosed and treated for UTI in the 6-week post-operative period following surgery
  - **General Demographic Data:**
    - Age, weight, height, BMI, ethnicity, past medical history, social history, preoperative stage of prolapse (POPQ), type of surgical procedure, duration of Foley catheter therapy, post-operative complications, UTI

symptoms, urine acidity (pH), diagnosis of overactive bladder, post void residual (PVR) before surgery, POD1 and on or about POD7.

- **Intervention or experimental aspect of the study**

- All patients of Cincinnati Urogynecology Associates who undergo pelvic organ prolapse repair(s) and have a retrograde VT prior to discharge per standard practice. The retrograde VT will be performed by the nursing staff. Per protocol, up to 300ml sterile saline will be instilled into the bladder and the indwelling urinary catheter will be removed. Patients will be allotted 30 minutes to void. The instilled volume, voided volume, and PVR if needed will be recorded.
- Failure of the retrograde VT is defined by inability to void two-thirds of the instilled volume or PVR greater than 100mL.
- Patients who fail the retrograde VT will then be approached for the study by one of the investigators or trained Research Nurse.
- An indwelling urinary catheter will be reinserted and the patient will be taught on its use and care by the nursing staff.
- If the patient agrees to participate in the study, the patient will be randomized to either receive either the MH and Cranberry or Cranberry and placebo.
- Based on a randomization list, the patient will be assigned a Study ID and the medications will be distributed by the inpatient pharmacy to the patient prior to their discharge.
- The medications will have a label which will be generated by the pharmacy that includes the name of the patient, name of the medication group allocation, (Ex. Med A) expiration date and study ID.
- These medications will be added onto their discharge instructions via a Medication Reconciliation on EPIC.
- All subjects will be provided all other routine prescriptions for pain medication, bowel regimen and instructions on how to administer the medication given.
- Patients will be advised to take the medication roughly at the same time each day with food to aid in absorption.
- On or about POD7, the patient will be asked to return to the office for a repeat retrograde VT (as described above).
- A catheterized urine specimen will be collected on this visit and recorded.
- If the patient fails the retrograde VT on or about POD7 they will have the catheter replaced. Additionally, they will be recommended to continue Cranberry supplementation as per our current routine practices until they return on their two-week postoperative visit to repeat the retrograde VT (as described above). They will however not be asked to continue MH or the placebo pills during this time.

- Patients will fill out a questionnaire based on the Medicine Acceptability Questionnaire as well as UTI symptoms experienced and overall satisfaction [43].
- Two-week postoperative visit
  - All patients will have a routine examination at 2 weeks with a clean catch urine specimen
  - All patients will have urine dip performed on the PVR urine sample. If positive for leukocyte esterase, white blood cells, or nitrites, the urine dip will be sent to the laboratory for culture. All urine culture results will be reviewed and if positive, will be treated and recorded.
- Six-week postoperative visit
  - All patients will be asked to present for routine 6-week post-operative visit.
- As per standard practice at our office, patients will be advised to report symptoms such as dysuria, fever, flank pain, hematuria, frequency or urgency, cloudy urine, hematuria, or abdominal pain,. During business hours they will be asked to call the office staff, while other times they will page the on-call physician.
- During operating hours, the office staff will arrange a clinic visit for the same day at one of four outpatient clinics (Clifton, West Chester, Kenwood, Anderson) and obtain a urine sample prior to the start of antibiotic therapy.
- If not during office hours, the on-call staff will either direct the patient to a facility for urine collection prior to the start of antibiotic therapy, or if unable to do so, start antibiotic therapy based on clinical symptoms.
- During any antibiotic therapy the patients will be advised to STOP all study medications
- All of these encounters will be recorded.
- **Experimental oral capsules**
  - Methenamine Hippurate 1g (1 tablet BID)
    - Contains Hippuric acid salt of Methenamine (hexamethylene tetramine), Magnesium Stearate, Povidone, Saccharin Sodium, FD&C Yellow No. 5 (Tartazine) [44].
    - >90% of methenamine is excreted in the urine within 24 hours after administration [44].
    - Side effects are generally mild and are found in 3.3% of patients. These include gastrointestinal upset, dysuria, abdominal cramps, and rash which are reversible [44].
    - Sulfonamides are to be used with caution with Methenamine as it has been shown that it concurrent use may cause a decrease in efficacy of the Methenamine by alkalization of the urine [44].
  - Placebo Pill

- Nature Made Super Strength Cranberry 450mg Extract (1 Tablet BID)
      - Side effects are generally mild and include stomach/abdominal upset, diarrhea. Kidney stones may occur but is associated with higher high doses [46].
      - There have been case reports regarding hypercoagulability with high doses of Cranberry concomitant Warfarin therapy [47].
  - Urinary Tract Infection (UTI) [48]
    - Definition will include bacteriuria will be presence of bacteria at clinically relevant levels, or treatment with antibiotic for suspected UTI by a provider
      - Possible associated symptoms patients may complain of include: dysuria, suprapubic pressure/pain, fever >100.4, urinary frequency or urgency.
- **Statistical Analysis**
  - Descriptive statistics will be generated for demographic information such as age, race, BMI etc. Chi-squared test or Fisher's exact test will be employed to examine the difference in categorical variables between two groups. A Shapiro-Wilk test will be performed for testing normality. To test the difference in continuous variables between two groups, Student t-test or a Mann-Whitney test will be used. A Logistic regression will be implemented to calculate the odds ratio and corresponding confidence interval for comparing the incidence of UTI between two groups.

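### Adverse effects are a secondary outcome, but the only between-arm analysis that reaches them is a generic significance test, with no estimate or interval for excess harm

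*Combined protocol and SAP*

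**What the plan says.** Under Data Collection in the Research Plan, the secondary outcomes include "Adverse effects that patients encountered during study period". No analysis is attached to that line.

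The Statistical Analysis text does not mention adverse effects. If they are recorded as yes or no for each patient, the sentence that reaches them is the general one: "Chi-squared test or Fisher's exact test will be employed to examine the difference in categorical variables between two groups". It gives no rule for choosing between the two tests. The one effect estimate with an interval is for efficacy: "A Logistic regression will be implemented to calculate the odds ratio and corresponding confidence interval for comparing the incidence of UTI between two groups".

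Two statements under Experimental oral capsules bear on the rates to expect. For MH: "Side effects are generally mild and are found in 3.3% of patients", cited to the package insert. For cranberry, which both arms take: "Side effects are generally mild and include stomach/abdominal upset, diarrhea", with no rate. The Sample Size text gives 88 per arm (104 enrolled after 15% drop-out), sized for UTI. It claims no power for adverse effects.

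**The concern.** MH is given here as prophylaxis, so its tolerability bears on whether adding it to cranberry is worthwhile. As written, the plan's only between-arm comparison of harm is a p-value. A p-value does not show how large an excess the data still allow, and with few events a non-significant result is likely even when a modest excess exists. A reader given only that p-value could not tell whether the trial had excluded an excess of 2 points or one of 10.

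**Working it through.** **Inputs.** From the documents: 88 evaluable and 104 enrolled per arm (Sample Size); a two-sided 0.05 level, stated for the sample size and assumed here for adverse effects; an MH side-effect rate of 3.3% (Experimental oral capsules). Assumed: the control-arm rate, taken over 0% to 10%, and that MH adds 3.3 points to it.

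**The plan's own figure.** The Background gives UTI rates of 38% and 19% from the cranberry trial that the Sample Size text cites. With mean rate p̄ = 0.285,

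n = [1.96·√(2·0.285·0.715) + 0.842·√(0.38·0.62 + 0.19·0.81)]² / 0.19² = 87.4, so 88 per arm.

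Then 88/0.85 = 103.5, so 104. Both figures reproduce, and they concern UTI only.

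**Power at 3.3% vs 0%.** With no control events and 88 per arm, Fisher gives p = 0.059 at 5 vs 0 and p = 0.029 at 6 vs 0, so it needs at least 6 events. Uncorrected chi-squared needs at least 4. The expected MH count is 88 × 0.033 = 2.9.

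- Fisher: P(X ≥ 6 | 88, 0.033) = 7.1%
- Uncorrected chi-squared: P(X ≥ 4 | 88, 0.033) = 33.1%

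**Power for the same 3.3-point excess at other control rates.** This sums the two binomial distributions over each test's rejection region.

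| Control → MH | Fisher, 88 | Chi-squared, 88 | Fisher, 104 | Chi-squared, 104 |
|---|---|---|---|---|
| 0% → 3.3% | 7.1% | 33.1% | 13.0% | 45.0% |
| 1% → 4.3% | 8.7% | 25.1% | 13.5% | 29.9% |
| 3.3% → 6.6% | 8.6% | 14.9% | 11.3% | 17.8% |
| 5% → 8.3% | 8.2% | 13.0% | 10.1% | 15.6% |
| 10% → 13.3% | 7.1% | 10.4% | 7.8% | 11.7% |

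**Power for larger excesses at 88 per arm.**

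| Control → MH | Fisher | Chi-squared |
|---|---|---|
| 3.3% → 10% | 32% | 42% |
| 0% → 10% | 88% | 98% |
| 3.3% → 15% | 73% | 81% |
| 3.3% → 20% | 94% | 96% |

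Fisher reaches 80% power at about 9% vs 0%, 16% vs 3.3%, 19.5% vs 5% and 27.5% vs 10%.

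**What an interval would show.** Take 3/88 on MH and 1/88 on control.

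- Fisher: p = 1 − C(88,2)²/C(176,4) = 1 − 14,653,584/38,630,900 = 0.62.
- Difference: 3/88 − 1/88 = 0.0341 − 0.0114 = 0.0227.
- Wilson 95% limits: 0.0117 to 0.0955 for 3/88, and 0.0020 to 0.0616 for 1/88.
- Newcombe lower limit: 0.0227 − √[(0.0341 − 0.0117)² + (0.0616 − 0.0114)²] = −0.032.
- Newcombe upper limit: 0.0227 + √[(0.0955 − 0.0341)² + (0.0114 − 0.0020)²] = +0.085.

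The same calculation for other counts, MH vs control:

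| Events (of 88 each) | Fisher p | Difference, points | Newcombe 95% interval |
|---|---|---|---|
| 3 vs 0 | 0.25 | +3.4 | −1.3 to +9.5 |
| 3 vs 1 | 0.62 | +2.3 | −3.2 to +8.5 |
| 6 vs 3 | 0.50 | +3.4 | −3.7 to +11.0 |

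None of these is significant, and each leaves an excess of 8 points or more possible.

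**The case against.** Low power for a secondary safety outcome is usual in a trial sized for efficacy, and this plan claims none. Any 2×2 test needs the counts by arm, so an interval could be computed at reporting even if none is planned. Both points stand. The shortcoming is reliance on a test alone, and it is one of presentation, not of design.

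A reader might infer that power is about 7% under either planned test. The documents do not support that. The figure needs Fisher, 88 per arm and no adverse effects at all in the control arm. Uncorrected chi-squared gives 33% on the same inputs, and the plan has no rule that selects Fisher. A zero control rate also sits badly with the cranberry side effects that the protocol lists for a product both arms take. Power for a 3.3-point excess does stay low at non-zero control rates.

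A reader might also infer that the test will miss harm almost whatever MH does, or that the trial will report no difference in safety. The first is wrong, since large excesses are detected with good power. The second is a prediction about reporting, and nothing in the plan says it.

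Finally, an interval is only as good as the count behind it. The plan gives no definition of an adverse effect and no attribution rule, and an interval does not supply them. Dysuria is listed both as an MH side effect and as a UTI symptom, and abdominal cramps overlap with the abdominal pain that patients are told to report. If MH prevents UTI, less infection-related dysuria could offset drug-related dysuria. That objection stands and shapes the fix.

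**Conclusion.** The concern holds as a minor one. A listed secondary outcome has no planned effect estimate or interval, and the generic test is weak for excesses near the rate that the protocol itself cites: about 7–9% power with Fisher and 10–33% with uncorrected chi-squared at 88 per arm. With 104 per arm analysed the ranges are about 8–14% and 12–45%.

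These figures rest on a two-sided 0.05 level, a control rate between 0% and 10%, and reading the package-insert 3.3% as an excess over control. The last two are assumptions. The case for an interval does not depend on them: at the example counts, p-values of 0.25 to 0.62 go with upper limits of +8.5 to +11.0 points. The conclusion is limited to modest excesses, and the efficacy analysis is unaffected.

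**What to change.** Add to the Statistical Analysis text:

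- For adverse effects, the main result is the number and percent of patients in each arm and the risk difference (MH minus placebo) with a Newcombe 95% confidence interval, overall and for each side effect that the protocol names. This replaces reliance on the chi-squared or Fisher test.
- A p-value above 0.05 will not be reported as evidence of equal safety.
- Dysuria and abdominal cramps are shown with a note that they overlap with the UTI symptoms listed in the protocol.

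I would not add a pass/fail criterion on the upper limit of the interval, because the documents give no limit to judge it against.

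The cost is small: a few sentences, with no new data and no change to sample size. The safety statement may read less favourably than a bare non-significant p-value, because it will show how much excess harm remains possible.

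### The bottle label prints a group name as well as the study ID; if one letter serves a whole arm, one disclosure would decode every other label that is then seen

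*Combined protocol and SAP*

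**What the plan says.** Under Study Design the trial is described as "Randomized double-blinded placebo-controlled trial". The Setting section defines two arms, both taking cranberry, with methenamine hippurate in one and placebo in the other. It also says "The research nurse will be blinded to the group allocation"; no other role is named as blinded.

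The section on the intervention says the study ID comes from a randomization list and the inpatient pharmacy dispenses. The label "includes the name of the patient, name of the medication group allocation, (Ex. Med A) expiration date and study ID". The same section adds: "These medications will be added onto their discharge instructions via a Medication Reconciliation on EPIC". Whether the group name appears in that entry is not stated.

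On where the label goes next, the Setting section says "Patients will be asked to return the pill bottles at their catheter removal visit, on or about postoperative day 7". It does not say who receives them.

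The primary outcome under Data Collection is "Incidence of UTIs requiring treatment in each group" over roughly the first week of catheterisation. A secondary outcome is "Number of patients who are diagnosed and treated for UTI in the 6-week post-operative period following surgery". The UTI definition, placed under the experimental capsules, can be met by bacteriuria or by a provider giving antibiotics for a suspected UTI.

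The documents do not say how many group codes exist, who holds the key, or how one patient's code would be broken.

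**The concern.** A label that carries only a patient-unique ID limits any disclosure to one patient. A label that also carries a code shared across an arm does not. With two arms and two letters, learning what one patient received decodes her letter and, by elimination, the other. Anyone who has that knowledge and then sees another patient's bottle can read her arm.

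What would be at stake is the part of the UTI outcome that depends on a provider's decision. Treatment for suspected UTI counts as an event, and bottles come back at the visit where the catheterised specimen is taken. A provider who knew the arm could, in principle, have a different threshold for treating at that visit or later in the 6-week follow-up. The group name adds nothing to identification, because patient name and study ID are already on the label.

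**Working it through.** **1. The plan's own figures.** They are checked because the steps below use them. Inputs: two-sided alpha 0.05 and power 80% (Sample Size section); rates 38% and 19%, which are an assumption, since that section cites the earlier cranberry trial without stating rates and the Background gives these two.

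n per arm = [z(0.975)·√(2p̄(1−p̄)) + z(0.80)·√(p₁(1−p₁) + p₂(1−p₂))]² / (p₁−p₂)², with p̄ = 0.285. This gives 87.4, rounded up to **88**, as stated. Dropout: 88/0.85 = 103.5, rounded up to **104** per arm and 208 in all, as stated.

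**2. How many patients one disclosure reaches.** These are ceilings, because only labels actually seen count.

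- One letter per arm: 104 − 1 = 103 others share the letter, and 104 more follow by elimination. Total 103 + 104 = **207**.
- Four codes, assumed evenly split: 208/4 − 1 = 51 others share the disclosed code. Eight codes: 208/8 − 1 = 25.
- Study ID alone, key kept in the pharmacy: **0**.

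This counts information that becomes readable, not outcomes that become biased. Outcomes already recorded before a letter is decoded cannot change.

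**3. What limited exposure could do to the primary test.** Assumptions, none of them in the documents: no true effect; 88 analysed per arm; a quarter of patients exposed; the recorded UTI rate among exposed patients in one arm lowered by 2 or 5 points. The control rate p runs from 19% (the cranberry group in the cited trial) to 72% (the institution's own retrospective review), both from the Background.

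Shift averaged over the arm: δ = 0.25 × 0.05 = 0.0125, or 0.25 × 0.02 = 0.005. With q = p − δ and p̄ = (p+q)/2:

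SE₀ = √(2p̄(1−p̄)/88); SE₁ = √((p(1−p) + q(1−q))/88)

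False-positive rate = Φ((δ − 1.96·SE₀)/SE₁) + Φ((−δ − 1.96·SE₀)/SE₁)

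At p = 0.19:

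- δ = 0.0125: SE₀ and SE₁ are both 0.0584. Φ(−1.746) + Φ(−2.174) = 0.0404 + 0.0148 = **0.055**.
- δ = 0.005: SE₀ and SE₁ are both 0.0588. Φ(−1.875) + Φ(−2.045) = 0.0304 + 0.0204 = **0.051**.

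| Assumed shift, a quarter exposed | False-positive rate, p from 19% to 72% |
|---|---|
| 2 points | 5.1% throughout (0.0505 to 0.0508) |
| 5 points | 5.3% to 5.5% |

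At a control rate of 10%, the low end of the Background's published range, the 5-point shift gives 5.9%. In patients, 5 points in a quarter of an arm is 0.0125 × 88 = 1.1 patients. These figures show size under stated assumptions and say nothing about how likely any shift is.

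**The case against.** The case against is strong on most counts.

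- **One code per arm is not stated.** Correct. It is the natural reading because the item is named as the group allocation and is listed apart from the study ID, but several codes per arm are not excluded. The reach would then be smaller, though still above zero.
- **The label does not contradict the blinding.** Correct. A reader might infer that printing the group name breaks the double blind, or conflicts with the research nurse being blinded. It does neither: a masked letter is compatible with both statements.
- **No disclosure is described.** Correct. The protocol urges caution when sulfonamides are combined with methenamine, which could prompt a request for one patient's arm. But patients are told to stop all study medication during any antibiotic therapy, an instruction that does not depend on the arm.
- **Room to influence the outcome is narrow.** Largely correct. The documented staff exposure comes at the end of the primary window, so earlier symptom calls and out-of-hours treatment lie outside it. Bacteriuria also meets the definition, and positive two-week cultures are treated. The Setting section says "Symptomatic or culture proven urinary tract infections detected during the research period will be treated with the appropriate antibiotics as standard of care"; its reference to provider judgment may govern only the choice of antibiotic.
- **A large inflation of the false-positive rate.** A reader might suppose that a whole arm could be affected. That needs a letter decoded before the first patient and influence on every recorded outcome. The documents support neither, so no such figure is given here.
- **Patient-reported symptoms and satisfaction.** A reader might extend the concern to these. No route is shown by which a patient would learn what her letter means.

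What remains is that the label carries an unneeded shared code, if it is shared, and that nothing in the plan confines one disclosure to one patient.

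**Conclusion.** The point holds as a low-priority, conditional improvement. If one letter is shared by an arm, a single disclosure would make up to 207 other patients' arms readable from their labels, against none with patient-unique codes. The consequence falls mainly on treatment decisions at the day-7 visit and afterwards. Under limited exposure it is small: about 5.1-5.5% instead of 5%, for an assumed shift of 2 to 5 points in a quarter of patients and a control rate of 19-72%.

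This rests on the one-letter-per-arm reading, on a disclosure the plan does not describe, and on the person who learns of it seeing other bottles and acting on what they show. It is not evidence that the blind fails. Sample size is unaffected.

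**What to change.** - Remove the group name from the label, and from the EPIC entry if it appears there.
- Identify the methenamine or placebo bottle by patient name, study ID, expiry and a neutral product name identical in both arms, for example: study drug, methenamine hippurate or placebo. The cranberry is the same in both arms and can be labelled as cranberry.
- State that the pharmacy alone holds the list linking study ID to arm, and breaks the code one patient at a time.

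Cost: one or two protocol sentences and a changed label template, with no change to sample size or visits. The downside is that the pharmacy must verify the product against the ID list instead of a group name. If the codes in use are already unique to each patient, one sentence saying so closes the point.

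### Does counting antibiotic treatment for suspected UTI as an event, with no culture-confirmed sensitivity analysis, undermine the primary comparison?

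*Combined protocol and SAP*

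**What the plan says.** All of this is in the Research Plan of the combined protocol and SAP.

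- **Primary outcome (Data Collection):** "Incidence of UTIs requiring treatment in each group", diagnosed in roughly the first week of catheterisation.
- **UTI definition (end of the intervention section):** two limbs. One is that "bacteriuria will be presence of bacteria at clinically relevant levels", with no numerical threshold. The other is "or treatment with antibiotic for suspected UTI by a provider".
- **Route to treatment:** in office hours staff are to "obtain a urine sample prior to the start of antibiotic therapy". Out of hours a specimen is sought first, and only "if unable to do so, start antibiotic therapy based on clinical symptoms". The encounters are recorded.
- **Side effects:** for MH, "These include gastrointestinal upset, dysuria, abdominal cramps, and rash which are reversible"; their overall frequency is given as 3.3%. For cranberry, which both arms take, "Side effects are generally mild and include stomach/abdominal upset, diarrhea". Dysuria is also among the possible UTI symptoms.
- **Exposure:** patients who fail the repeat void trial around day 7 keep a catheter, but "They will however not be asked to continue MH or the placebo pills during this time".
- **Statistical Analysis:** chi-squared or Fisher's exact test for categorical variables, and a logistic regression giving an odds ratio with confidence interval for UTI. No sensitivity analysis of the UTI outcome is listed.

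**The concern.** The two limbs are joined by an alternative, so suspicion plus a prescription is enough. Nothing removes an episode whose culture proves negative, and an out-of-hours episode may have no culture at all. Every participant goes home with a catheter, which can itself cause symptoms. MH can cause dysuria, which is also a UTI symptom.

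If some treated patients have no infection, two things could follow. Equal numbers of such episodes in both arms shrink the difference, and an excess confined to the MH arm shrinks it further. With power planned at only 80%, a null result might then mean either that MH does not work or that its effect was diluted. A single planned comparison could not tell these apart.

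**Working it through.** **1. Reproducing the plan's figure.** Inputs: 38% and 19%, the placebo and cranberry UTI rates of the earlier cranberry trial (Background); two-sided 5% chi-squared test, 80% power and 15% drop-out (Sample Size). The Sample Size section names that trial without restating its rates, so their use here is an inference.

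n = [1.960·√(2p̄(1−p̄)) + 0.8416·√(p₁(1−p₁)+p₂(1−p₂))]² / (p₁−p₂)², with p̄ = 0.285

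= (1.960×0.6384 + 0.8416×0.6241)² / 0.0361 = 3.156/0.0361 = 87.4, so 88 per arm. Then 88/0.85 = 103.5, so 104. Both match the plan. Power at 88 per arm is 80.3%.

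**2. Dilution relative to proven infection.** Suppose a share f of patients without true infection is treated in each arm. Then p′ = p + (1−p)f, and the difference shrinks by the factor (1−f). The documents give no f, so these values are assumptions.

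| f | Control | MH | Odds ratio | Power at 88 |
|---|---|---|---|---|
| 0 | 38.0% | 19.0% | 0.38 | 80.3% |
| 2% | 39.2% | 20.6% | 0.40 | 77.4% |
| 5% | 41.1% | 23.1% | 0.43 | 73.1% |
| 10% | 44.2% | 27.1% | 0.47 | 66.1% |

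The arithmetic is sound, but it treats 38% and 19% as free of unconfirmed episodes. The documents do not give the earlier trial's UTI definition. If it was similarly broad, the 80% already includes this dilution.

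**3. The MH-only excess.** Scoring every MH side effect as a UTI, with none in controls, gives 0.19 + 0.81×0.033 = 21.7% and power 66.0%. That counts rash as a UTI, so it is not a realistic figure. At one tenth of it (0.33%, assumed) power is 79.0%.

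**4. Is the planned comparison valid for its own endpoint?** Set the outcome beside the definition. The outcome is infection requiring treatment, and the Background gives reduced antibiotic use as a goal. A treated suspected UTI is such an event. An antibiotic course prompted by MH-induced dysuria is likewise a real consequence of MH. If MH has no effect on treatment, the two arms have the same event probability and the test keeps its 5% error rate.

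**5. Would a culture-confirmed analysis resolve a null result?**

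- *Power.* If 80% of true infections are confirmed (assumed), the rates are 0.8×38% = 30.4% and 0.8×19% = 15.2%, and power is 67.4%. That is below the 73.1% of the primary analysis at f = 5%.
- *Bias.* The Background describes MH as bacteriostatic in the bladder. Suppose there is no true benefit and culture positivity is 10% or 20% lower on MH (assumed). Then 38% against 34.2% or 30.4% is significant 8.2% or 18.5% of the time instead of 5%. Starting from 30.4% in controls, the figures are 7.3% and 14.7%.
- *Specificity.* The Background quotes about 5% more bacteriuria per catheter day. Over 7 days that is 7×5% = 35% if additive, or 1−0.95⁷ = 30% if compounded (my reading of the figure). Some patients with irritation alone would therefore be culture-positive and stay in the analysis.

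A null primary result beside a positive culture-only result could thus reflect diluted benefit or suppressed cultures. The ambiguity would remain.

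**The case for a change.** The best case for the concern grants that the primary outcome is defensible and asks only for a supportive analysis beside it. The Background criticises earlier MH studies for differing UTI definitions, so this trial might be expected to show whether its own result depends on the definition. Blinding does not prevent equal dilution or symptoms caused by the drug. The extra work appears small because encounters are recorded and specimens usually precede antibiotics. Choices made after the data are seen also carry less weight.

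Much of this is true. The definition does admit unconfirmed episodes, no sensitivity analysis is listed, and dilution relative to proven infection runs in the direction claimed. A stated bacterial threshold, recorded culture results and a count of unconfirmed episodes by arm would help readers.

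Three things limit it. First, these are additions to reporting; none corrects the planned comparison. Second, the cost may be understated: the plan requires a specimen before antibiotics but does not say that every such specimen is cultured, and it describes culture after a positive dipstick only at the two-week visit. Third, the route to treatment with no specimen is narrow, being out of hours and only when collection is impossible.

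**Conclusion.** The concern does not hold as a fault in the plan. The endpoint is treated UTI, the definition fits it, and the planned comparison is valid for it. The loss of power from 80% to 77%, 73% or 66% arises only against a different endpoint, at assumed rates of 2%, 5% or 10%, and only if the planning rates contain no such episodes. The proposed culture-confirmed analysis has lower power under the 80% confirmation assumption and its own possible bias toward MH, so it could not separate absence of benefit from diluted benefit.

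The conclusion assumes that treatment decisions are effectively blinded. The Research Plan calls the trial double-blinded, although it names only the research nurse as blinded and has the medication labelled by coded group. It also takes the primary outcome as written. If the trial were later presented as showing an effect on culture-proven infection, the definition would not support that claim.
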